9.4 Sample Size Considerations

The primary comparison will include all eligible and treated patients, of whom 135 will be accrued and randomized equally, for a total accrual of 67 patients per arm. After adjusting for an ineligibility rate of 10%, the total required sample size for randomization is 150 patients. Using an overall one-sided 0.10 level log rank test, this study will have 88% power to detect a 37.5% reduction in the PFS hazard rate of 0.139 to 0.087 based on the estimated accrual and follow-up period. Assuming an exponential survival, this corresponds to a 60% improvement in the median PFS of 5 months on CE to 8 months on CE plus nivolumab. The number of PFS events needed to achieve this power is 113 events under the alternative hypothesis.

Correlative Study Statistical Considerations:

Tumor DNA levels obtained from the serial collection of cfDNA samples will be examined to explore whether clinical outcome is associated with fluctuations in DNA levels following the administration of therapy. Plasma will be collected from 30 patients on each arm of the study at baseline and cycle 2 day 1.

A variety of statistical techniques will be employed for the analyses of cfDNA. The rate of change at a particular time point may be compared to baseline measures of cfDNA and that measure will be analyzed for association with subject demographics and/or disease characteristics using the Kruskal Wallis test. Landmark analyses of PFS and OS in which the landmark time is defined by the cfDNA measurements at a particular time point, may be used as well. Presence or absence of mutations in plasma will be analyzed for association with other variables using Fisher's exact test. To account for the repeated measures of plasma over time, we may potentially use these data as time varying covariates in multivariable Cox models to study their impact on outcomes like PFS and OS. Models would be adjusted for known prognostic factors and treatment arm; we will also fit a marker by treatment interaction, though it is difficult to power for an interaction test in this setting. If we are to dichotomize patients according to the median change in plasma levels from baseline to a second timepoint such as end of chemotherapy, with at least 60 patients in the analysis we would have 85% power to detect a difference in induction response rates of 40% among those with low plasma response and 80% among those with high plasma response while testing with a one-sided 0.025 level Fisher's exact test.

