2.3 Exploratory objectives

2.3.1 To evaluate immune biomarkers and biomarkers correlates

2.3.2 To evaluate serial circulating tumor DNA and explore whether clinical outcome is associated with fluctuations in DNA levels following the administration of therapy.

3. Selection of Patients

Each of the criteria in the checklist that follows must be met in order for a patient to be considered eligible for this study. Use the checklist to confirm a patient's eligibility. For each patient, this checklist must be photocopied, completed and maintained in the patient's chart.

In calculating days of tests and measurements, the day a test or measurement is done is considered Day 0. Therefore, if a test is done on a Monday, the Monday four weeks later would be considered Day 28.

ECOG-ACRIN Patient No. _____

Patient's Initials (L, F, M) _____

Physician Signature and Date _____

NOTE: CTEP Policy does not allow for the issuance of waivers to any protocol specified criteria (http://ctep.cancer.gov/protocolDevelopment/policies_deviations.htm). Therefore, all eligibility criteria listed in Section 3 must be met, without exception. The registration of individuals who do not meet all criteria listed in Section 3 can result in the participant being censored from the analysis of the study, and the citation of a major protocol violation during an audit. All questions regarding clarification of eligibility criteria must be directed to the Group's Executive Officer ([contact]) or the Group's Regulatory Officer ([contact]).

NOTE: Institutions may use the eligibility checklist as source documentation if it has been reviewed, signed, and dated prior to registration/randomization by the treating physician.

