11.1 Circulating Tumor DNA Qualification and Sequencing

Rev. Add1

We will collect peripheral blood at baseline and cycle two, day one. Circulating tumor DNA will be measured quantitatively and total exonic mutation burden will be assessed with whole exome sequencing using the Guardant360 platform that will inform on allelic frequency of mutations, mutational burden, and specific targeted exome sequencing and amplification of relevant cancer related genes. Baseline nonsynonymous mutation burden, neo-antigen burden and DNA repair pathway mutations will be correlated with response to immunotherapy.

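### The one cfDNA-by-response comparison with a stated power cuts the plasma change at its median; if the association is graded, a rank test on the uncut change has about 13 points more power in the same 60 patients

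*Combined protocol and SAP*

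**What the plan says.** Section 11.1 makes the measurement continuous: "Circulating tumor DNA will be measured quantitatively". Objective 2.3.2 is to "explore whether clinical outcome is associated with fluctuations in DNA levels following the administration of therapy". For the sample, section 9.4 says: "Plasma will be collected from 30 patients on each arm of the study at baseline and cycle 2 day 1".

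The correlative paragraphs of 9.4 then give a single power statement, and its opening is conditional: "If we are to dichotomize patients according to the median change in plasma levels from baseline to a second timepoint". The sample for that case is put at 60 or more. The assumed response proportions are "40% among those with low plasma response and 80% among those with high plasma response". The stated power is 85%, and the test is named in the closing words: "while testing with a one-sided 0.025 level Fisher's exact test".

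The same paragraphs list other cfDNA methods, mostly as options:

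- Kruskal-Wallis tests of the change against demographics and disease characteristics
- landmark analyses of PFS and OS
- Fisher's test for presence of mutations
- Cox models with plasma as a time-varying covariate

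None of these carries a power figure, and none relates plasma change to response. Section 9.3 assigns the Wilcoxon rank-sum test to continuous outcomes and logistic regression to categorical ones such as response. Section 9.4 does not connect either method to plasma change by response.

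**The concern.** A median split treats a patient just above the median like one with an extreme change, so it discards the size of the change within each half. The cut-point is also specific to the sample and does not carry over to another study. Fisher's exact test then runs below its nominal level at 30 against 30, which costs further power.

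Only about 60 patients are planned to supply plasma. The efficiency of the test therefore bears on whether a real association would be seen. No reason is given for the cut, and the plan already has a rank method for continuous data.

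**Working it through.** **Inputs.** From 9.4: 60 patients, so 30 per half after a median split; response 40% and 80%; Fisher's exact test; one-sided 0.025. Assumed: the shape of the relation between plasma change *x* and response.

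**1. The plan's figure.** With X1 ~ Bin(30, 0.40) and X2 ~ Bin(30, 0.80), power is the sum of P(X1 = a)·P(X2 = b) over all (a, b) for which P(H ≥ b) ≤ 0.025. Here H is hypergeometric: 30 drawn from 60, of whom a + b are responders. Result: **85.1%**, against 85% stated. It reproduces.

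**2. Graded association.** P(response | x) was made a smooth increasing function, solved so that mean response is exactly 0.40 below and 0.80 above the median of x. For example, with normal x, logit P = 0.532 + 1.269x. In each simulated set of 60 patients, two tests were applied:

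- Fisher's test on the sample-median split
- the Wilcoxon test on uncut x: z = [W − m(N+1)/2] / √[m(N−m)(N+1)/12], with N = 60, m responders and W their rank sum; reject if z > 1.96

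Results from 40,000 trials each (gaps taken before rounding):

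| Shape | Fisher on split | Wilcoxon, uncut | Gap (points) |
|---|---|---|---|
| logit, normal x | 84.2% | 97.9% | 13.7 |
| probit, normal x | 83.8% | 98.0% | 14.2 |
| logit, uniform x | 83.8% | 96.5% | 12.7 |
| linear, uniform x | 84.1% | 97.4% | 13.3 |
| logit, lognormal x | 83.7% | 97.5% | 13.7 |
| logit, t (3 df) x | 84.2% | 98.2% | 14.1 |

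Fisher falls slightly below 85.1% because the sample median varies around the true one. Under the first shape, the Wilcoxon test needs about 36 patients for 85% power.

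**3. Where the gap comes from.** A mid-p version of Fisher's test on the same split removes most of its conservatism without undoing the cut (100,000 trials each):

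| Shape | Fisher | Mid-p, same split | Wilcoxon | Due to Fisher | Due to the cut |
|---|---|---|---|---|---|
| logit, normal x | 83.8% | 89.1% | 97.7% | 5.3 | 8.6 |
| linear, uniform x | 83.8% | 89.2% | 97.4% | 5.4 | 8.2 |
| logit, uniform x | 83.6% | 89.0% | 96.4% | 5.5 | 7.4 |

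Under the null (response 0.60 throughout), the attained level is about 1.4% for Fisher, 2.5% for mid-p and 2.5% for Wilcoxon.

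**4. Step association.** If response jumps from 40% to 80% exactly at the sample median, Fisher has 85.1% and Wilcoxon 80.7%: the split gains 85.1 − 80.7 = 4.4 points. If the jump is at the population median instead, Fisher has 75.0% and Wilcoxon 79.4%.

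**The case against.** **The split is hypothetical.** This stands. A reader might infer that the plan commits to the median split as its test of cfDNA against response. The wording is conditional, and 9.4 leaves room for several methods. What remains is that this is the only scenario with a power figure and the only comparison of plasma change with response that is described.

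**The gradient is assumed.** This also stands. A reader might infer that about 16% of true associations are missed where 2-4% need be, simply from the 40% and 80% given. Those two rates do not supply a shape. Read literally as two constant rates split at the sample median, they favour Fisher's test. The larger gain needs a gradient within each half; in the logit-normal case, response runs from about 17% at the 5th percentile of x to 93% at the 95th.

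**The cut is not the whole cause.** Correct: 5-6 points belong to Fisher's conservatism, a known property of an exact test and not an error in the plan.

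**The PFS and OS models.** A reader might infer that the landmark and Cox analyses also use the split. No section says so, and the time-varying Cox option mentions no cut. Those analyses need no correction on this ground.

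**The remedy is nearly in the plan.** Section 9.3 already names the Wilcoxon test and logistic regression. That makes the change a clarification, but 9.4 does not apply either to this question, so a sentence is still needed.

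**Undetectable cfDNA would create ties.** With 20%, 30% and 40% of patients tied at the favourable extreme, simulated Wilcoxon power at 60 patients was 97.7%, 97.3% and 96.6%. The rank test tolerates ties; a logistic model on the change needs a stated rule.

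**Conclusion.** The point holds as a low-cost improvement to an exploratory analysis. The stated 85% is correct. If the scenario in 9.4 is used and the association is graded, testing the uncut change raises power from about 84% to about 96-98% in the same 60 patients, a gain of roughly 13-14 points. About 7-9 of these come from not cutting and 5-6 from leaving Fisher's test.

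The size rests on the assumed shape. It was stable across six smooth shapes and reverses, by about 4 to 5 points, only for a step exactly at the sample median. The primary PFS test, the interim look and the sample size are untouched.

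**What to change.** In the correlative paragraphs of 9.4:

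- Name the Wilcoxon rank-sum test on the uncut change from baseline to cycle 2 day 1, responders against non-responders, one-sided 0.025 with the direction stated, as the cfDNA-response analysis. Cycle 2 day 1 is the only post-baseline draw that the plan schedules.
- Support it with a logistic model for response on the continuous change, adjusted for treatment arm, with a stated rule for undetectable values.
- Keep the median split for descriptive tables and plots.
- State power under both shapes: with 60 paired samples and mean response of 40% and 80% below and above the median change, about 96-98% for a graded association and about 81% for a step at the sample median.

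The cost is a few sentences, with no new patients, samples or assays. The price in power is about 4 to 5 points if the truth is a step exactly at the sample median.

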9.5 Projected Accrual

As reflected by previous ECOG SCLC studies, it is estimated that patient accrual will be approximately 9 patients per month. It is estimated that the accrual goal

will be reached within approximately 15 months with a follow up period of approximately 10 months, for total study duration of 25 months.

9.6 Randomization Scheme

Randomization to treatment will be determined using permuted blocks within strata with dynamic balancing on main ECOG-ACRIN institutions plus affiliates. The randomization will be stratified by gender (Male vs. Female) and LDH (WNL vs. > upper limit of normal).

9.7 Monitoring Plan

9.7.1 Interim Analysis: Efficacy

This study will also be monitored for futility and one interim analysis at roughly 50% information is planned. At that time, if the point estimate of the PFS hazard ratio is consistent with detriment (HR > 1.0), then the data monitoring committee may consider terminating the study early for overall lack of treatment difference.

9.7.2 Interim analyses of toxicity are performed twice yearly for all ECOG-ACRIN studies. Reports of these analyses are sent to the ECOG-ACRIN Principal Investigator or Senior Investigator at the participating institutions. Expedited reporting of certain adverse events is required, as described in Section [5.2](#).

9.8 Gender and Ethnicity

Based on previous data from **E2511** the anticipated accrual in subgroups defined by gender and race is:

PLANNED ENROLLMENT REPORT						
Racial Categories	Ethnic Categories				Total	
	Not Hispanic or Latino		Hispanic or Latino			
	Female	Male	Female	Male		
American Indian/ Alaska Native	0	0	0	0	0	
Asian	0	2	0	0	2	
Native Hawaiian or Other Pacific Islander	0	0	0	0	0	
Black or African American	0	4	0	0	4	
White	74	70	0	0	144	
More Than One Race	0	0	0	0	0	
Total	74	76	0	0	150	

The accrual targets in individual cells are not large enough for definitive subgroup analyses. Therefore, overall accrual to the study will not be extended to meet individual subgroup accrual targets.

10. Specimen Submissions

Peripheral blood specimens are to be submitted per patient consent for defined laboratory research studies described in Section [11](#).

Tumor tissue specimens are to be submitted per patient consent for future undefined research studies.

All specimens must be clearly labeled with the ECOG-ACRIN protocol number (EA5161), the patient's initials and ECOG-ACRIN patient sequence number, the collection date, and specimen type

It is required that all specimens submitted on this trial be entered and tracked via the ECOG-ACRIN Sample Tracking System (STS) (Section [10.3](#)). An STS shipping manifest form is to be included with every submission.

10.1 Submissions to the ECOG-ACRIN Central Biorepository and Pathology Facility (CBPF)

If you have any questions concerning tumor tissue and peripheral blood submissions please contact the ECOG-ACRIN CBPF at [contact] or [contact]

10.1.1 Pathological Material Submissions

Submit from patients who answer "Yes" to "I agree to provide additional samples for research."

Representative tumor tissue specimens from the pretreatment diagnostic biopsy are to be submitted for undefined research studies (per patient consent) within one (1) month of randomization.

Submitting pathologist and clinical research associate may refer to [Appendix I](#) which outlines the Pathology Submission Guidelines.

The tumor tissue specimens are to be labeled with the institution's assigned pathology ID# as well as the information above.

10.1.1.1 Required Materials

Forms: Must be submitted with all pathology submissions.
STS generated shipping manifest form
Copy of the institutional pathology report
Immunological study reports, if available

Tumor Tissue Submission:

Formalin-fixed paraffin-embedded (FFPE) tumor tissue block

NOTE: If blocks are unavailable for submission, cores and slides are to be submitted. All cores and slides must be adequately labeled, with slides numbered sequentially in the order cut.
Alternative submission requirements:

- One (1) H&E slide

- Twenty (20) 5 µm unstained, uncharged, air-dried plus slides from the thickest part of the tumor
- One (1) or more core punches (minimum of 4mm diameter). If core punch tool is unavailable, request core punch kit from the ECOG-ACRIN CBPF [contact]. Adequately label every slide and core submitted.

If these criteria cannot be met, please contact the ECOG-ACRIN CBPF ([contact]) to obtain alternative submission requirements.

10.1.2 Peripheral Blood Submissions

Submit from patients who answer 'Yes' to 'I agree to have my samples collected and I agree that my samples and related information may be used for the laboratory studies.'

Kits for the collection and shipment of the peripheral blood specimens are ordered online from Cenetron Central Laboratories. Instructions are provided in [Appendix VII](#). Questions regarding kits can be directed to [contact] or call the Cenetron Clinical Trials Group at [contact]. Kits must be ordered after the patient has been randomized to the trial and will generally arrive within three (3) business days from when the order was placed.

10.1.2.1 Specimen Preparation Guidelines

Peripheral blood specimens are to be collected at the following time points:

- Prior to Start of Treatment
- Cyce Two (2), Day One (1)

Streck Cell-Free DNA Tubes

- Draw two (2) 10mL Streck Cell-Free DNA BCT tubes of whole blood at each time point. Fill each tube completely.
- Ensure at least 10mL of blood is drawn. Avoid low volume to minimize agitation during shipping.
- Immediately after collection, gently invert tube 180 degrees and back 10 times to ensure adequate mixing.
 - Maintain blood at room temperature (6°C to 37°C) until shipping. **Do Not** place tubes in refrigerator.

10.1.3 Shipping Procedures

Pathology materials are to be shipped at ambient temperature within one (1) month following randomization.

Peripheral blood specimens are to be shipped at ambient temperature Monday-Thursday via overnight courier.

Friday shipments are ill advised, similarly shipping before holidays is often problematic. The laboratory is closed Saturday, Sunday, and holidays.

Ship using the CBPF's FedEx account using the FedEx online ship manager

Ship to:

ECOG-ACRIN Central Biorepository and Pathology Facility
MD Anderson Cancer Center
Department of Pathology, Unit 085
Tissue Qualification Laboratory for ECOG-ACRIN, Room G1.3598
[name]
[name]
Phone: Toll Free [contact] [contact] Local or International Sites)
[contact]
Email: [contact]

Access to the FedEx shipping account for shipments to the ECOG-ACRIN CBPF at MD Anderson Cancer Center can only be obtained by logging onto fedex.com with an account issued by the ECOG-ACRIN CBPF. For security reasons, the account number will no longer be given out in protocols, over the phone, or via email. If your institution needs to have an account created, please contact the ECOG-ACRIN CBPF by email at [contact]

An STS shipping manifest form must be generated and shipped with all specimen submissions.

Rev. Add1

10.2 Use of Specimens in Research

See Section [11](#) for the description of the laboratory research studies to be performed.

Specimens (tumor tissue and blood leftover after the laboratory research studies) from patients who consented to allow their specimens to be used for future undefined ECOG-ACRIN approved research studies will be retained in an ECOG-ACRIN designated central repository.

For this trial, specimens will be retained at the ECOG-ACRIN Central Biorepository and Pathology Facility.

Specimens submitted will be processed to maximize their utility for current and future research projects. Tissue processing may include, but not limited to, extraction of DNA and RNA and construction of tissue microarrays (TMAs). DNA, RNA, serum, and plasma (if appropriate) will be isolated from the submitted peripheral blood specimens.

Any residual blocks will be available for purposes of individual patient management on specific written request.

If future use is denied or withdrawn by the patient, the specimens will be removed from consideration for use in any future research study. Pathology materials may be retained for documentation purposes or returned to the institution. All other specimens will be destroyed per guidelines of the respective repository.

10.3 ECOG-ACRIN Sample Tracking System

It is **required** that all specimens submitted on this trial be entered and tracked using the ECOG-ACRIN Sample Tracking System (STS). The software will allow the use of either 1) an ECOG-ACRIN user-name and password previously assigned (for those already using STS), or 2) a CTSU username and password.

When you are ready to log the collection and/or shipment of the specimens required for this study, please access the Sample Tracking System software by clicking <https://webapps.ecog.org/Tst>

Important: Please note that the STS software creates pop-up windows, so you will need to enable pop-ups within your web browser while using the software. A user manual and interactive demo are available by clicking this link:
<http://www.ecog.org/general/stsinfo.html>

Please take a moment to familiarize yourself with the software prior to using the system.

An STS generated shipping manifest form should be shipped with all specimen submissions.

Please direct your questions or comments pertaining to the STS to
[contact]

Study Specific Notes

Generic Specimen Submission Form (#2981v3) will be required only if STS is unavailable at time of specimen submission. Notify the laboratory of the shipment by faxing a copy of the completed form to the laboratory.

Retroactively enter all specimen collection and shipping information when STS is available.

10.4 Sample Inventory Submission Guidelines

Inventories of all specimens submitted will be tracked via the ECOG-ACRIN STS and receipt and usability verified by the receiving laboratory. Inventories of specimens forwarded and utilized for the approved laboratory research studies will be submitted by the investigating laboratories to the ECOG-ACRIN Operations Office - Boston on a monthly basis in an electronic format defined by the ECOG-ACRIN Operations Office - Boston.

11. Laboratory Research Studies

Results of these studies are for the purposes of the trial only and will not be returned to the institution or reported to the patient.

11.1 Circulating Tumor DNA Qualification and Sequencing

Rev. Add1

We will collect peripheral blood at baseline and cycle two, day one. Circulating tumor DNA will be measured quantitatively and total exonic mutation burden will be assessed with whole exome sequencing using the Guardant360 platform that will inform on allelic frequency of mutations, mutational burden, and specific targeted exome sequencing and amplification of relevant cancer related genes. Baseline nonsynonymous mutation burden, neo-antigen burden and DNA repair pathway mutations will be correlated with response to immunotherapy.

